### 3.1 Discussion of study design

The current study design is explorative in nature and will deliver descriptive data on the potential for long-term retention of gadolinium in human bone. Restricting the study population to patients with stable normal renal function is unlikely to provide further insight into the mechanism of Gd retention and the potential development of NSF. Therefore, subgroups with different degrees of renal decrement are included.

A limitation of the study is the retrospective nature of data associated with the single or multiple administration of the GdCAs. It is anticipated that some of the specified analytical clinical and laboratory parameters will not be available within the patient records. However, it would be impossible to prospectively assess potential Gd retention in patients with moderate and

severe decrement in renal function, because the administration of GdCAs to such patients is now limited due to regulation.

The current study, therefore, will enrol patients who received a specified GdCA at least 1 month prior to an orthopaedic surgery procedure and will prospectively collect bone and skin samples for analysis. Conducting the study in patients who plan to undergo a medically indicated orthopaedic surgery procedure provides an accessible model for collecting samples without adding a significant interventional load onto the patients. The collection of bone and skin biopsies are required to correlate Gd content in bone and skin with potential histopathological findings associated with NSF.

GdCA-naïve patients will be included as controls for any background concentration of Gd in bone, e.g. from the environment. For example, Gd has been found in skin biopsies of NSF patients who were considered to be “gadolinium-free” (23), as well as in bone samples from patients with no previous exposure to GdCA (21).

In summary, the study design is adequately selected to contribute to the understanding of long-term Gd retention in patients who receive GdCAs. The study design was developed through scientific discussions with the EMA/ CHMP.

## 4 SELECTION OF STUDY POPULATION

In this study a minimum of 99 evaluable patients (see 8.1.1) will be recruited, according to the distribution per Assessed GdCA/Renal function status depicted in table 1.

The patients will be recruited in at least 35 centres in America, Europe and Asia. Each patient must meet all inclusion criteria and not present any exclusion criteria.

### 4.1 Patient inclusion criteria

Each patient must fulfil the following criteria to be eligible for the study:

1. Patient must be at least 18 years of age (or older if required by local regulations)
2. Patient scheduled for an orthopaedic surgical procedure provided that the required amount of trans-operative collection of bone and skin as defined per-protocol in section 5.1.3 is feasible and all inclusion and no exclusion criteria are met.
3. Patient is scheduled to have sufficient bone removed during the orthopaedic surgical procedure and sufficient non-scarred skin tissue from the edge of the surgical incision or amputated part to permit sample collection, in the investigator's medical opinion
4. Patient agreed to have bone and skin samples collected at the time of the surgical procedure(s)
5. Patient's surgical procedure and subsequent remission will not be altered by study-specific skin biopsies, in the investigator's medical opinion
6. Patient is fully informed about the study and has signed the informed consent form

### Patients having received GdCA

7. Patient belongs to one of the following subgroups with respect to the number of GdCA doses received and the status of their renal function:
  - a) patient (total to enrol = 5) has **stable impaired renal function** (at least moderate impairment, eGFR  $\leq$  60 ml/min/1.73 m^2) and has received **one GdCA injection** at the standard dose (0.025 mmol per kg body weight for Gadoxetic acid and 0.1 mmol per kg body weight for all other agents)

or

b) Up to 5 patients with **stable impaired renal function** (at least moderate impairment, eGFR  $\leq$  60 ml/min/1.73 m $^2$ ) and has received **more than one injection** of the same GdCA.

- Gadodiamide, Gadopentetic acid, Gadoversetamide, and Gadoxetic acid groups: no target number. Patients should be recruited to this subgroup throughout the study duration, but there is no requirement to reach a specific number of patients in this subgroup to achieve study completion.
- Gadobutrol and Gadoteric acid groups: at least 3 patients. If the target of 3 patients is reached, but the study has not yet completed, then recruitment to this group should be continued during the remaining study time.

or

c) patient (total to enrol = 5) has **stable normal renal function** (eGFR  $>$  60 ml/min/1.73 m $^2$ ) and has received **one GdCA injection** at the standard dose (0.025 mmol per kg body weight for Gadoxetic acid and 0.1 mmol per kg body weight for all other agents)

or

d) patient (total to enrol = 3 to 5) with **stable normal renal function** (eGFR  $>$  60 ml/min/1.73 m $^2$ ) who have received **more than one injection** of the same GdCA. If the target of 3 patients is reached, but the study has not yet been completed, then recruitment to this subgroup should be continued during the remaining study time, stopping when 5 patients have been recruited to this subgroup, or when all other subgroups have reached their minimum target for recruitment, whichever comes first.

8. A minimum of 1 month have elapsed between GdCA dose and the scheduled orthopaedic surgical procedure.

9. Patient GdCA history, including dose(s), date(s), and product(s) administered is complete and accurate.

#### **GdCA naïve patients (control group)**

10. Patient has never received GdCA before the scheduled orthopaedic surgical procedure.

11. Patient belongs to one of the following renal function categories:

- e) patient (total to enrol = 5) has stable severe renal impairment (eGFR  $<$  30 ml/min/1.73 m $^2$ );
- f) patient (total to enrol = 5) has stable moderate renal impairment (eGFR within the range 30 to 60 ml/min/1.73 m $^2$ );
- g) patient (total to enrol = 5) has stable normal renal function (eGFR  $>$  60 ml/min/1.73 m $^2$ ).

#### **4.2 Patient exclusion criteria**

No patient may enter the study if any of the following exclusion criteria are fulfilled:

1. Patient has received different GdCAs.
2. Patient has received intra-articular GdCA or per any other non-i.v. route.

3. Patient has received or is scheduled to receive GdCA within 1 month prior to the date of the scheduled orthopaedic surgical and study sample collection procedures.

4. Patient has received any investigational product or has participated in any other clinical trial within 30 days prior to enrolling in this study.

5. Patient suspected of, or diagnosed with, tumour of the skeletal system (i.e. tumour, metastatic bone, and bone marrow disease in the region from where the skin and bone will be harvested).

*Note: Patients shall not be excluded for other bone diseases with the exception of those with bone cancer as specified in exclusion criterion 5.*

6. Patient has diagnosed or suspected NSF at time of enrolment.

*Note: Patients shall not be excluded for diagnosis of NSF subsequent to enrolment.*

7. Patient presents with scarring in the region(s) of the scheduled surgical procedure(s) or of the skin sampling location, to the extent that collection of an unscarred skin sample is not feasible.

8. Patient has a close affiliation with the investigational site; e.g., a relative of the investigator, dependent person (e.g., employee or student of the investigational site).

#### 4.3 Patient withdrawal criteria

An enrolled patient must be withdrawn from the study immediately if any of the following occurs:

- During screening: if the enrolment group for which the patient qualifies, has already been closed.
- Patient requires a prohibited concomitant medication, including the administration of a GdCA after enrolment.
- Patient withdraws consent.
- An illness occurs during the study period that is likely to influence the assessment of the study in the investigator's medical opinion (i.e. patient is suspected of, or diagnosed with, tumour of the skeletal system (e.g. in knee / hip bone, metastatic bone and bone marrow disease in knee / hip or other location where the orthopaedic surgery is to be performed)).

Furthermore, an enrolled patient may be withdrawn prematurely from the study, at the investigator's discretion, under the following circumstances:

- One of the inclusion criteria listed in section 4.1 does not apply.
- One of the exclusion criteria listed in section 4.2 applies.
- Patient does not cooperate adequately to permit study procedures and assessments.
- Any adverse event (AE) after which a continuation in the study would constitute an unacceptably high risk for the patient.
- Investigator determines it is in the best interest of the patient to withdraw from the study.

The Sponsor should be informed of any decision to withdraw an individual patient. If possible, a complete final examination according to the visit schedule should be carried out and documented on the corresponding pages of the electronic case report form (eCRF) for

those patients prematurely discontinuing the study. Although patients may withdraw from the study at any time without giving any reasons and without prejudice to future treatment, efforts should be made to document the reason for withdrawal in each case.

Instructions for patient follow-up in case of withdrawal due to an AE are described in section 6.2.4.3.

Withdrawal criterion for patients undergoing multiple GdCA doses:

- If a patient undergoes a second orthopaedic surgical procedure that would qualify for the collection of bone and skin as described elsewhere in the protocol section 5.1.3 (e.g. hip or knee surgery) during the study period, and the patient receives any additional dose of a GdCA between the first and the second surgical procedure, the patient must be withdrawn from the study. No additional bone and skin samples shall be collected during the second surgery for the study. However, the data and tissue samples obtained in connection with the first surgery, prior to administration of disqualifying GdCAs, will be used for the statistical evaluation.

## 5 STUDY TREATMENTS, PRODUCTS AND INTERVENTIONS

### 5.1 Products administered

#### 5.1.1 Products administered prior to enrolment

##### 5.1.1.1 Products under evaluation

Patients in the test groups (a to d) must have received only one of the following GdCAs, at least 1 month prior to scheduled orthopaedic surgery on study:

1. Gadobutrol (Gadovist®, Gadavist® & Gadograf®);
2. Gadodiamide (Omniscan®);
3. Gadopentetic acid (Magnevist®);
4. Gadoteric acid (Dotarem® & Magnescope®);
5. Gadoversetamide (Optimark®);
6. Gadoxetic acid (Primovist®, Eovist® & EOB-Primovist®)

Patients in the control groups e), f) and g) must be treatment-naïve regarding any GdCA.

##### 5.1.1.2 Dosage of products under evaluation

- 0.1 mmol per kg body weight for the products 1–5: GdCAs with the active ingredients Gadobutrol, Gadodiamide, Gadopentetic acid, Gadoteric acid, and Gadoversetamide; subgroups a) and c).
- 0.025 mmol per kg body weight for the product 6: GdCAs with the active ingredient Gadoxetic acid; subgroups a) and c).
- Actual doses injected for all multiple doses subgroups for all products 1–6; subgroups b) and d).

##### 5.1.1.3 Dosing frequency

- Single GdCA dose (one injection) at least 1 month prior to the scheduled orthopaedic surgical procedure; products 1–6: subgroups a) and c).

- Multiple doses (more than one injection) of the same GdCA, regardless of frequency. Last GdCA dose at least 1 month prior to the scheduled orthopaedic surgical procedure; products 1–6: subgroups b) and d).

#### 5.1.1.4 Route of administration

- Intravenous only

#### 5.1.2 Products administered after enrolment

None

*Note: No GdCA will be administered to the patients during the study by the investigators.*

#### 5.1.3 Prospective study interventions

Patients must be scheduled for orthopaedic surgery (e.g. hip or knee replacement surgery, limb amputations and shoulder replacement) before enrolment in the study. This surgical intervention for the patient's underlying condition will be completed during the study; however, the surgical procedure itself is not a study-driven intervention.

The scheduled skin biopsy is the only interventional procedure to be performed to patients participating in this study (i.e. the only procedure performed for study purposes and not part of the otherwise necessary care of the patients). This biopsy will be performed during the scheduled orthopaedic surgical procedure. Bone samples will be collected from a surgically removed bone specimen and therefore not considered being a study-related intervention. If a patient is scheduled for a second orthopaedic surgical procedure that would qualify for the collection of bone and skin as described in this section (e.g. hip or knee surgery), additional bone and skin samples will be collected.

##### Bone tissue sampling:

Bone tissue will be collected from bone removed during the scheduled orthopaedic surgical procedure. A portion of the removed bone (e.g. the heads of femoral or tibial bone, whichever is removed during surgery), will be further processed ex-vivo. At surgical site, two aliquots will be taken, each with a minimum weight of 15 g. Further bone sample handling will be done in the bioanalytical central laboratory to harvest two samples from each aliquot, one consisting of trabecular and the other of cortical bone. Bone samples will precisely be weighed and analysed in the central bioanalytical laboratory (for the concentration of Gd, Ca, P, Na, Zn, K and Fe).

##### Skin tissue sampling:

Skin samples will be collected from the incisional site made for the scheduled orthopaedic surgical procedure or amputated part if applicable. A parallel linear sample of tissue will be cut from one edge of the incision wound to the other. It should be 2 mm thick, and as long as the incision (typically at least 10 cm of length, according to surgical practice). Depth should be the depth of the skin to the fascia (4 mm is a conservative estimate; the linear incision will be no longer or deeper than it would have been without removing a sample). Since thickness and depth of skin tissue slices are kept constant, the maximum amount of skin tissue collected is defined by the length of the surgical incision. The wound is closed in accordance to the sites' clinical practice.

From the linear sample, two aliquots of 5 mm length each are required for later histopathological analysis and will be evaluated in the central histopathology laboratory by an experienced and independent (blinded) dermatopathologist in order to identify any skin changes associated with NSF.

The remaining linear sample will be divided into two aliquots for later bioanalytical analysis (yielding approximately 320 mg of fresh tissue per aliquot). The aliquots will be weighted and analysed in the central bioanalytical laboratory for the concentration of Gd, Ca, P, Na, Zn, K and Fe.

## 5.2 Method of assigning patients to treatment groups

No randomisation of patients to treatments applies. However, ad-hoc stratification of patients to the enrolment groups will be managed centrally (see 5.5).

## 5.3 Selection of dose and timing for each patient

This protocol focuses on the exploration of long-term Gd-retention in patients exposed to GdCAs. There is no upper limit for the time-interval between GdCA administration and sample collection during the scheduled orthopaedic surgical procedure, based on prior evidence that Gd may be detectable in bone 8 years after injection of GdCA (21). In this protocol, the time interval between the last dose of GdCA and surgery must be at least 1 month. The enrolment of patients with a wide range of times between GdCA injection and time of tissue sample collection during surgery may support the evaluation of long-term Gd-retention.

The study will evaluate for the subgroups with a history of single GdCA dose administration only patients who received the approved standard dose for each of the GdCAs. For the products with the active ingredients Gadobutrol, Gadodiamide, Gadopentetic acid, Gadoteric acid, and Gadoversetamide this is 0.1 mmol per kg body weight. For Gadoxetic acid, a single dose is 0.025 mmol per kg body weight.

Patients in the respective multiple doses subgroups will have received either repeated doses or a single or multiple higher than the approved standard dose, and thus higher cumulative concentrations of the same GdCA. Any higher dose than 120% of the standard dose of GdCA will be analysed as part of the multiple doses subgroup. In both dose subgroups, the individual and total combined doses administered will be documented and evaluated.

## 5.4 Supply, packaging and labelling

Since qualifying GdCA was administered prior to patient enrolment, no supply of any study medication is required in the present study. Therefore, neither storage, shipment, packaging, nor labelling are applicable.

## 5.5 Blinding and randomisation

There will be no randomisation. The analysis of bone and skin tissue samples will be done in a blinded manner.

Patients will be registered centrally via an interactive web response system (IWRS). This system will be connected with the eCRF and will be accessible 24 hours/7 days a week. Each patient will be assigned to a stratified enrolment group defined by the GdCA ingredient administered (or control), renal function category (moderate impairment, severe impairment or stable normal renal function eGFR > 60 ml/min/1.73 m^2) and dosing number (single / multiple). Confirmation of patient enrolment will be provided to the enrolling centre and shall be retained by the investigator.

Once a stratification group is complete, no further enrolment into that group will be allowed. All participating centres will be notified upon the completion of each enrolment group.

The data of all patients on study will be de-identified by allocation of a patient number to each patient enrolled. No identifying information will be contained in the study eCRF. Patient numbers will be issued sequentially to each centre upon patient enrolment.

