**Number of patients**  
 At least 99 evaluable patients will be included.

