## 3 OVERALL STUDY DESIGN AND PLAN DESCRIPTION

This is a multicentre, retrospective, prospectively interventional and exploratory, post authorisation study which will be conducted globally evaluating the potential for long-term retention of Gd in bones of patients who received single or multiple doses of GdCAs. The study is retrospective with respect to GdCA administration (no GdCA will be administered to patients during the study by the investigator), prospective with respect to bone sample collection (taken from surgically removed bone) and both, prospective and interventional regarding skin sample collection. Skin sampling is required for both dermatopathological assessment and quantification of Gd.

Patients aged at least 18 years (or older if required by local regulations) who are scheduled for an orthopaedic surgery procedure (provided that the required amount of trans-operative collection of bone and skin as defined in section 5.1.3 is feasible and all inclusion and no exclusion criteria are met) and agree to provide bone and skin samples at the time of the procedure will be included in the study after they sign a written informed consent form. In this study, a minimum of 99 evaluable patients will be enrolled, from which at least 84 patients have received GdCA (test group) and 15 patients have never received GdCA (control group) prior the orthopaedic surgery procedure.

The products assessed are GdCAs which include one of the active ingredients Gadobutrol, Gadodiamide, Gadopentetic acid, Gadoteric acid, Gadoversetamide or Gadoxetic acid. Figure 1 and Table 1 describe enrolment targets per GdCA and the stratification of patients that will be prospectively controlled (see 5.5).

**Figure 1:** Target number of patients per GdCA

For the test group, GdCA products must have been administered intravenously at least one month prior to the orthopaedic surgery procedure. Only patients for whom information regarding the active ingredient of the specific GdCA, the name of the product, the date(s) of administration and the dose(s) of the administered GdCA are available will be enrolled. Patients who received GdCAs containing any other active ingredient will not be enrolled. Furthermore, documentation of stable renal function prior to administration of the GdCA is required, and renal function must have been assessed at least once within approximately 3 months prior to GdCA injection.

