#### 8.1.11 Determination of sample size

There are no prior expectations or assumptions relative to the measured concentrations of Gd in the bone (primary objective) and in skin (secondary objective). Due to the exploratory nature of the study, the sample size was not determined based on formal statistical consideration, but rather on the feasibility of conducting the study as a whole. The study is intended to be analysed descriptively. No formal hypothesis testing is planned.

There are six groups for active GdCA ingredients (Gadobutrol, Gadodiamide, Gadopentetic acid, Gadoteric acid, Gadoversetamide, and Gadoxetic acid).

In each group, three categories of renal function (stable (normal) renal function (eGFR > 60 ml/min/1.73 m^2) versus impaired renal function (eGFR <30 ml/min/1.73 m^2 (severe) and ≥30 to <=60 ml/min/1.73 m^2 (moderate)) and two subgroups of dosing of GdCA (single / multiple) are to be evaluated.

Per active GdCA ingredient the recruitment targets are defined as follows

- 5 patients for stable normal renal function (eGFR > 60 ml/min/1.73 m^2) and single dose
- at least 3 patients and up to 5 patients for stable normal renal function and multiple doses
- 5 patients for impaired renal function (eGFR <=60 ml/min/1.73 m^2) and single dose
- up to 5 patients for impaired renal function (eGFR <=60 ml/min/1.73 m^2) and multiple doses. For Gadobutrol and Gadoteric acid, at least 3 patients are required. For Gadodiamide, Gadopentetic acid, Gadoversetamide, and Gadoxetic acid, there is no requirement to reach a specific number of patients to achieve study completion.

The total number of patients enrolled in these groups will be at least 84.

The number of subgroups in the GdCA-naïve population is 3 according to renal function category (i.e. severe or moderate impairment, and stable normal renal function). Five patients will be enrolled per each sub-group. Therefore, the total number of GdCA-naïve patients enrolled will be at least 15.

Consequently, a minimum of 99 patients in total shall be included in the study.

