8.7 Interim Analysis

At the request of the EMA, an interim analysis was to be carried out on all subjects enrolled in the single dose subgroups for Gadobutrol, Gadoteric acid, Gadodiamide, and Gadopentetic acid once at least three subjects had been recruited to the single-dose subgroups for the 4 agents as well as on all subjects of the control group (naïve subjects).

A total of 55 subjects were eligible for the IA. Due to the fact, that the laboratory data for these subjects had to be unblinded, these subjects have already been classified before IA evaluation with regard to PDs. Since one subject had no concentration data available, only 54 subjects were included in the SAF.

To determine the Gd concentration in bone (trabecular and cortical) and skin (expressed as $\mu\text{g Gd / g}$) the IA based on the SAF and Gd concentrations was descriptively evaluated by:

- Renal function status: stable normal renal function ($\text{eGFR} > 60 \text{ ml/min/1.73 m}^2$),
 at least moderate impaired renal function ($\leq 60 \text{ ml/min/1.73 m}^2$)
- GBCA: Each of the 4 GBCAs (Gadobutrol, Gadoteric acid, Gadodiamide, and Gadopentetic acid) and control

No statistical tests have been calculated.

All data used in the interim analysis have been listed. All listings including subject identifier, GBCA type, renal function, and have been sorted by GBCA type, renal function, and subject identifier. Study investigational sites and analytical laboratories have been blinded to the IA results.

Details on the IA evaluation have been described in the interim SAP and the Abbreviated Interim Analysis Report, Version Final 1.0, dated 20181108.

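### The stated minimum of 99 evaluable patients is a sum of enrolment minimums with no stated allowance for loss, so the design does not assure the evaluable size, least of all in the single-dose cells

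*Protocol*

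**What the plan says.** Three places in the protocol attach the word *evaluable* to the total:

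- Synopsis: "At least 99 evaluable patients will be included".
- Section 3: "a minimum of 99 evaluable patients will be enrolled".
- Section 4: "a minimum of 99 evaluable patients (see 8.1.1) will be recruited". The cross-reference is to the analysis populations.

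SAP 7.1 repeats the evaluable minimum of 99.

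The sections that build the number count enrolled patients. Protocol 8.1.11 gives at least 84 enrolled in the exposed groups and, for the controls, "Five patients will be enrolled per each sub-group". Its closing total of 99 does not carry the word evaluable. In Protocol 4.1, the single-dose categories of criterion 7 begin "patient (total to enrol = 5) has".

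On timing, Protocol 7.1 and 7.2.2 place IWRS registration at Visit 1, within 3 days before surgery. Under 4.3 and 7.2.2, a patient whose group is already full must be withdrawn. Protocol 5.5 sets the closing rule: "Once a stratification group is complete, no further enrolment into that group will be allowed". Protocol 8.1.1 leaves evaluability to a blinded data review before final unblinding. The FAS needs a bone gadolinium measurement. The per-protocol set also needs results for trabecular bone, cortical bone and skin, and full eligibility.

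**The concern.** An evaluable count and an enrolled count can be the same number only if nobody is lost between registration and analysis. The documents themselves foresee losses. Protocol 4.3 lists mandatory withdrawals after enrolment, SAP listing 16.2.1.1 is reserved for enrolled subjects whose surgery did not take place, and SAP 8.4 removes subjects with major deviations from the PPS. Neither document says how such losses would be made up.

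Two things are at stake. One is an accurate account of what was planned: a report that repeats 99 evaluable as the planned minimum would claim more than the sample-size section supports. The other is cell size. Results are tabulated by agent, renal function and dose category, and in a cell of 5 one loss is a fifth of the data.

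**Working it through.** **Reproducing the plan's figure** (Protocol Table 1 and 8.1.11)

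- Four agents: 5 + 0 + 5 + 3 = 13 each, so 4 × 13 = 52.
- Gadobutrol and gadoteric acid: 5 + 3 + 5 + 3 = 16 each, so 2 × 16 = 32.
- Exposed: 52 + 32 = 84. Controls: 3 × 5 = 15. Total: 84 + 15 = 99.

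The evaluable minimum therefore equals the enrolment minimum, which implies a loss of 0%.

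**Where there is slack**

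- Single-dose cells: 6 agents × 2 renal categories = 12 cells with a target of 5, or 60 places. Table 1 gives no range.
- Multiple-dose cells: minimum 84 − 60 = 24, ceiling 12 × 5 = 60, so up to 36 extra places.
- Ceiling with controls at 15: 6 × 20 + 15 = 135. A fully recruited study would expect 99 evaluable at any loss up to 1 − 99/135 = 26.7%.

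**Chance that the single-dose cells stay whole**

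No loss rate is planned, so d is an assumption. The only observed figure is in SAP 8.7: "Since one subject had no concentration data available, only 54 subjects were included in the SAF". With 55 subjects eligible for the interim analysis, that is 1/55 = 1.8%. The 5% and 10% rows show a range. Losses are taken as independent with the same d in every cell.

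| d | One cell keeps 5: (1−d)^5 | Cells expected short: 12 × [1 − (1−d)^5] | All 60 evaluable: (1−d)^60 |
|---|---|---|---|
| 1/55 (1.8%) | 0.912 | 1.1 | 0.33 |
| 5% | 0.774 | 2.7 | 0.046 |
| 10% | 0.590 | 4.9 | 0.002 |

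The controls are left out of this table because the documents do not hold them to a fixed number (see the objection).

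**The case against.** Several stronger readings are tempting, and the documents do not support them.

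- **That the design cannot deliver 99 evaluable patients.** The totals are minimums, and the multiple-dose cells can take the study to 135. The total is reachable. However, recruiting to the ceiling is not required, the normal-function multiple-dose cells may stop once all other subgroups reach their minimums, and this room is not described as a loss allowance.
- **That a cell closes on five enrolled patients.** Protocol 5.5 does not define completion, and section 4 ties the evaluable total to the distribution in Table 1. Enrolled is the more natural reading, because the check is made at Visit 1 and evaluability is settled much later with no described feedback to the IWRS. It remains an inference.
- **That the 15 control places are also fixed.** Protocol 8.1.11 says at least 15. SAP 8.6 says at least 5 normal and at least 10 impaired, while SAP 8.2.2 says up to 10 impaired. They cannot be treated as three cells of exactly 5.
- **That 89 to 97 evaluable should be expected.** Multiplying 99 by 0.90 gives 89.1 and by 54/55 gives 97.2, but this assumes that enrolment stops at the minimum and uses loss rates the plan does not contain. The 1/55 counts only missing concentration data among interim-eligible subjects, not all losses from enrolment to the PPS.
- **That every PPS exclusion damages the primary bone results.** SAP 9.6.1 runs the primary analysis on the FAS as well as the PPS, and the FAS does not need skin data.

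It is also fair that registration falls only days before an already scheduled operation, and that the bone tables will show N for both sets. What stands is the mismatch between the promised and the counted quantity, and the absence of any rule for loss.

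**Conclusion.** The point holds in a limited form: 99 is an enrolment minimum labelled as evaluable, and the evaluable size is not assured. In the 12 single-dose cells the chance of keeping all 60 places evaluable runs from about 33% to 0.2% as the assumed loss goes from 1.8% to 10%. This rests on independent losses, a common rate, and cells closing on enrolment. If closing was in fact on evaluable patients, the single-dose figures fall away, but the text still needs to say so. Surplus multiple-dose patients can repair the total and not a closed single-dose cell.

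The consequence is modest. The study was sized on feasibility and tests no hypothesis, so what suffers is the accuracy of the stated size and the precision of small cells.

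**What to change.** 1. Restate 99 as the minimum number enrolled in the synopsis, Protocol sections 3 and 4, and SAP 7.1.
2. Define *evaluable* by naming the analysis set, FAS or PPS.
3. In Table 14.1.1, report enrolled, FAS and PPS counts for each agent, renal-function and dose cell, and for the controls, beside the target. SAP 9.1 currently lists screened, enrolled, completed and discontinued subjects, without analysis-set counts or targets.

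Do not add a forecast of the evaluable number, because the plan holds no loss rate to support one. Changing the IWRS closing rule would achieve nothing now: SAP 7.1 gives recruitment as ending in December 2018.

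The cost is a few sentences and extra columns in one table. The stated size becomes slightly less favourable.
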